Hypothesis: We anticipate that the use of a venous closure device will decrease the time to hemostasis (TTH), time to ambulation (TTA) and time to discharge (TTD) compared to conventional methods of closure following venous access procedure.

III. Study Design & Methodology

This study will be a prospective, randomized study of patients who are undergoing one or more of the following procedures at ASLMC:

Large-Bore Procedures >13 F

- 1. WATCHMAN® device placement
- $2.\ Atrial\ fibrillation/flutter/SVT\ ablation\ using\ cryoballoon\ or\ laser\ balloon$
- 3. Leadless pacemaker
- 4. Pulmonary embolism thrombectomy (Inari FlowTriever system)
- 5. MitraClip transcatheter mitral valve repair

RANDOMIZATION:

Patients will be randomized into one of two venous closure groups after a clean stick has been achieved with no complications:

Large-bore (14F-25F) venous access group (1:1)
Perclose proglide smc
Figure 8 suture

Prior to enrollment a series of 110 randomization envelopes will be put together in a 1:1 to determine the closure strategy – Figure 8 suture or Perclose ProGlide SMC closure device for the large-bore procedures. Study investigators will draw an envelope to determine what group the subject will be randomized to only after sheath access has been achieved with no complications. Access should be ultrasound guided to guarantee a clean stick.

If randomization does not occur or if a complication not related to the Perclose ProGlide SMC closure device happens during the procedure the subject will be withdrawn from the study and considered a screen failure.

For both Perclose ProGlide SMC and figure 8 suture, supplemental manual compression may be used following device/suture placement if needed. If at any time the physician decides to use an alternate standard of care method as the primary method to achieve hemostasis other than that which the patient was randomized to, they may do so, and the patient will be considered a screen failure.

We will collect demographic data, past medical history, medication at the time of procedure, lab values at the time of procedure and post procedure, the need for blood transfusion, procedure details, and outcomes post procedure. *Study variables are listed in detail in the attached Excel file*.

Table 1: Schedule of Study Events:

Study Procedure	Screening	Day of Procedure	Follow-up (30 days post procedure)
Inclusion/exclusion	X		
Informed Consent		X	
Randomization to determine closure strategy		X	

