Data collection (medical history/baseline demographics, medications, lab values, procedure details, and outcomes post procedure)		X	X

IV. Eligibility

Inclusion criteria:

Large-bore (>13F) Venous Access Procedures Inclusion Criteria:

All patients 18 years and older who are undergoing any of the following: WATCHMAN® device placement, atrial fibrillation ablation using cryoballoon or laser balloon, leadless pacemaker, Pulmonary embolism thrombectomy (Inari FlowTriever system), MitraClip transcatheter mitral valve repair at Aurora St. Luke's Medical Center from date of IRB approval through December 2022. All arterial line access should be radial.

Exclusion criteria:

Large-bore (>13F) Venous Access Procedures Exclusion Criteria:

- Patients in whom introducer sheaths >25F were used in the vein during the catheterization procedure.
- Patients with small femoral arteries or veins (< 5 mm in diameter).
- Patients with access sites in vascular grafts.
- Patients with intra-procedural bleeding around access site. Patients who cannot receive radial arterial line access.
- Patients who have complications during the procedure not related to the Perclose ProGlide SMC closure device
- The physician determines that they must use an alternate method as the primary venous closure method other than that which the patient was randomized to
- Active systemic or cutaneous infection, or inflammation in vicinity of the groin
- Pre-existing immunodeficiency disorder or chronic use of high dose systemic steroids
- Known history of bleeding diathesis, coagulopathy, hypercoagulability or platelet count < 100,000 cells/mm3
- Severe co-existing morbidities with life expectancy less than 12 months

- Femoral arteriotomy or femoral venotomy in < 10 days, or with any known vascular complications or residual hematoma, or with use of an intravascular closure device w/in previous 30 days
- Planned femoral venous or arterial access within next 30 days
- Unable to routinely walk at least 20 ft. without assistance
- LMWH within 8 hours before or after procedure
- Pregnant and/or lactating women
- Extreme morbid obesity (BMI > 40 kg/m2) or underweight (BMI < 20 kg/m2)

V. Subject Enrollment

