An interim monitoring plan to perform periodic checks of the data after the first 25 subjects are enrolled and then again after 75 subjects are enrolled will be reviewed by the Biostatistician or study team to determine data integrity, accuracy, and consistency with the study objectives/hypotheses as well as preliminary analysis.

X. Statistical Considerations

A convenient sample size of approximately 55 subjects in each of the two randomized groups (Perclose ProGlide SMC and figure 8 suture) was determined to allow for parametric statistical methods. Following interim analysis: O'Brien-Fleming method was selected to adjust the p-value for interim analysis and final analysis. It was also used to calculate the required sample size at each stage of analysis in order to achieve 80% power in the outcome. Final sample size required was determined at 101 subjects. A 10% +/- should be added, to bring the total enrollment to 110 subjects.

XI. Outcomes

Primary outcomes: time to achieve hemostasis (TTH) and time to ambulate (TTA)

Secondary outcomes: time to discharge (TTD)/length of stay, post procedure major bleeding, mortality due to vascular complications, minor bleeding, access site hematoma, vascular thrombosis, vascular dissection, pseudoaneurysm, or AV fistula.

TTH: The elapsed time between "device" removal and first observed and confirmed venous hemostasis.

TTA: The elapsed time between removal of the final Perclose ProGlide SMC device (treatment arm) or removal of the final sheath (control arm), and the ability of subjects to stand and ambulate 20 feet without evidence of venous re-bleeding from the femoral access sites.

TTD/LOS: The elapsed time between removal of the final sheath, and the ability of subjects to be discharged. Length of hospital stay.

Major bleeding: Bleeding associated with ≥ 2 g/dl drop in hemoglobin level requiring transfusion, bleeding that occurs at a critical site, or bleeding contributing to death.

Minor Bleeding: Any bleeding that does not meet the criteria for major bleeding.

XII. Regulatory Requirements

Approval from the Aurora Health Care IRB will be obtained to perform this study, which includes approval of all associated informed consent forms. All protocol modifications and corresponding informed consent forms will be submitted for review and approval prior to implementing.

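### Section III ties the envelope draw to sheath access and sets no latest time, so unblinded operators may know the arm during the procedure and patients can be removed after allocation for events before closure

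*Combined protocol and SAP*

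**What the plan says.** Section III (Randomization) gives the trigger twice. The first statement is: "Patients will be randomized into one of two venous closure groups after a clean stick has been achieved with no complications". The second names who acts and when: study investigators "draw an envelope to determine what group the subject will be randomized to only after sheath access has been achieved with no complications". Neither statement mentions closure, and neither gives a latest time for the draw.

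The next paragraph of Section III deals with events in the procedure: "if a complication not related to the Perclose ProGlide SMC closure device happens during the procedure the subject will be withdrawn from the study", and the patient is counted as a screen failure. The same label applies if the physician switches to a primary closure method "other than that which the patient was randomized to, they may do so, and the patient will be considered a screen failure".

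Section IV repeats both rules as exclusion criteria. It adds use of a sheath above 25F during the procedure, and "Patients with intra-procedural bleeding around access site".

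Section XI makes TTH and TTA the primary outcomes. TTH runs from device removal, with the word device left undefined. TTA starts at "removal of the final Perclose ProGlide SMC device (treatment arm) or removal of the final sheath (control arm"). No section describes blinding of operator, patient or assessor, and none states when either closure method is first placed.

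**The concern.** The randomized comparison is between two ways of closing the vein. If the envelope is opened at access, an operator who cannot be blinded to the method carries that knowledge through a whole procedure in which it may not be needed. Two things follow.

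- **Conduct.** Choices made before closure can differ by arm because the arm is known. Such differences arise after randomization, so they cannot be safely adjusted away, and they remain even if every randomized patient is analyzed.
- **Removal.** Criteria that would be ordinary pre-randomization exclusions at the end of the procedure become post-allocation removals. Staff who know the arm decide them, and one rule asks whether a complication relates to the device used in only one arm. The groups analyzed are then no longer simply the groups randomized.

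**Working it through.** **1. When may the envelope be opened?** Both triggers in Section III are minimum conditions tied to access. Opening at closure satisfies them, and so does opening straight after access. The plan therefore permits early opening without requiring it. The withdrawal rule for complications in the procedure reads as if allocation is already known by then, since it turns on relation to ProGlide, but it does not settle the point.

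**2. Is the arm needed before closure?** Section XI starts TTA at ProGlide device removal in one arm and at final sheath removal in the other. If ProGlide were removed before the cardiac procedure, TTA in that arm would contain the whole procedure. The definition thus implies removal at the end. No section says when the device or the suture is first placed, so an earlier arm-specific step is not excluded.

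**3. Which removals depend on the time of opening?**

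| Rule | Opened at access | Opened at closure |
|---|---|---|
| Sheath above 25F used | can be after allocation | before allocation |
| Access-site bleeding in the procedure | after allocation | before allocation |
| Complication in the procedure, not ProGlide-related | after allocation | before allocation, unless it occurs during closure |
| Switch of primary closure method | after allocation | still after allocation |

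**4. Room for losses.** Section III provides 110 envelopes and does not say that used ones are replaced. Section X requires 101 subjects: 110 − 101 = 9. A tenth loss leaves 100.

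**5. Power under assumed loss.** Section X states no effect size or SD, so the 101 cannot be recomputed. Solving backwards from 101 subjects (50.5 per arm), two-sided alpha 0.048 and 80% power gives d = 0.567 SD by the t-test. The normal approximation gives (1.977 + 0.842) × √(2/50.5) = 0.561. With d = 0.567 and assumed losses of 0, 5, 10 and 15% of 110:

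| Assumed loss | Subjects left | Power |
|---|---|---|
| 0% | 110 | 83% |
| 5% | 104 | 81% |
| 10% | 99 | 79% |
| 15% | 94 | 77% |

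**6. False positives under an assumed shift.** Take a two-sided t-test with N = 101, 99 degrees of freedom, alpha 0.048 (Section IX) and no true closure effect. The critical value is 2.002. A mean shift of b SD gives a noncentrality of b × √(50.5/2).

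| Assumed shift b | Noncentrality | Chance of p < 0.048 |
|---|---|---|
| 0 | 0 | 4.8% |
| 0.1 | 0.50 | 7.6% |
| 0.2 | 1.00 | 16.4% |
| 0.3 | 1.51 | 31.4% |

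The documents support no particular value of b. The calculation applies to any bias from knowing the arm, including bias after closure.

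**The case against.** The sponsor can fairly answer as follows.

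- **The text sets only a minimum.** A reader might infer that the envelope must be opened at sheath access. The wording does not say so, and a site that opens it at closure already complies. This stands: the defect is the missing latest time.
- **The route to bias is thinly documented.** A reader might infer that operators manage everything affecting hemostasis, such as anticoagulation and its reversal, with the arm known. Apart from the LMWH exclusion, the documents say nothing about anticoagulation around the procedure. They describe no discretion over the number of sheaths or the timing of their removal. Arm-aware conduct is possible, but its content and size are not in the plan. This stands.
- **Much of the discretion comes after closure.** Supplemental compression, confirming hemostasis and judging ambulation all follow closure, when the arm must be known. Later opening leaves them untouched. This stands, and it limits what the change can achieve.
- **Later opening may not be feasible.** Section III separates complications in the procedure by relation to ProGlide, which leaves room for a device step before the end. This stands as a condition, and it is why the time of placement has to be stated first.
- **The allowance covers some loss.** The plan already adds 9 subjects to 101, and a 5% loss leaves 104. True for power, but the allowance does nothing about removals decided with the arm known.

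**Conclusion.** The concern holds in a limited form. The plan ties the draw to access, sets no latest time and describes no blinding. It therefore permits arm-aware conduct before closure and post-allocation removal for events before closure. Later opening would avoid most of both if nothing arm-specific is done earlier. The TTA definition suggests that condition is met, but no passage states it.

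The size cannot be derived from the documents. The rates of 7.6%, 16% and 31% rest on assumed shifts. A reader might take them as the benefit of moving the envelope. They are not, because bias after closure would remain. Nor is 0.567 SD the plan's effect size: it is back-solved from 101 subjects and 80% power, and the power figures inherit that along with the assumed loss rates. The one firm figure is the margin of 9 losses among 110.

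The amendment is worth making, with medium confidence. It is a partial remedy: the method-switch screen-failure rule and the different TTA starts by arm are separate problems that it does not solve.

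**What to change.** In Section III:

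1. State when each closure method is first placed, and reconcile this with the TTA definition in Section XI.
2. If nothing arm-specific is done before closure, have the operator record continued eligibility at the end of the procedure (no sheath above 25F, no access-site bleeding, no complication). Then open the envelope immediately before sheath removal for closure and log the clock time.
3. If an arm-specific step does come earlier, open the envelope at the latest moment before that step and log the time.
4. Analyze everyone whose envelope was opened in the arm assigned.

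Cost: a minor amendment to one step on the day of procedure, with a timestamp and a short eligibility record, and no added patients. The small downside is that the closure device is prepared later.

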Recruitment and consent are required since it is a prospective study. Patients will be identified for potential enrollment in this study from the lab schedules at Aurora St. Luke's Medical Center. The potential subjects medical record will be screened to determine eligibility. Patients found to be eligible will be considered for enrollment and may be contacted prior to the procedure to assess interest in participation.

VI. Specimen/Data Collection and Procedures

The source of data for this study will be the electronic medical record (Epic, Madison, WI). Only people included in this IRB will access the compiled data. Medical record information generated after the approval of this IRB will be collected up until the conclusion of the study.

VII. Risks, Protection & Benefits

Risks/adverse events as reported in the IFU – these complications may occur and/or be related to the procedure or the vascular closure:

- Allergic response
- Anemia
- Arterial stenosis/occlusion
- Arterio-venous fistula
- Bleeding from the puncture site
- Bruising/hematoma
- Death
- Device failure/malfunction/misplacement
- Device Entrapment
- Diminished pulses distal to closure site
- Hypotension/hypertension
- Edema
- Embolism
- Pulmonary Embolism
- Numbness
- Infection/sepsis
- Inflammatory response
- Intimal tear/dissection
- Ischemia distal to closure site
- Perforation of the vessel wall
- Nerve injury
- Pseudoaneurysm
- Retroperitoneal hematoma/bleeding
- Deep vein thrombosis
- Vascular injury
- Vasovagal episode
- Vasoconstriction/vasospasm
- Wound dehiscence
- Pain

• Thrombus formation

Risks of figure 8 suture method:

- Pain
- Pressure
- Hematoma
- Bleeding
- Vessel rupture
- Surgery

Benefits:

Depending on the closure strategy subjects may experience a decrease in bedrest time post procedure with potentially less complications.

Results of this study may also be generalizable to the larger healthcare community by informing standard of care guidelines for obtaining hemostasis and post procedure outcomes following the procedures studied in this protocol.

VIII. Adverse Event Reporting

Definitions

Adverse event: Any untoward medical occurrence, unintended disease or injury or untoward clinical signs in subjects, users, or other persons, whether or not related to the medical device.

Serious adverse event: Any adverse event that led to

- Death
- Life-threatening illness or injury
- Permanent impairment
- Prolonged hospitalization or change to inpatient status

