- Requires medical or surgical intervention to prevent life-threatening illness or injury or permanent impairment
- Fetal distress, fetal death, or congenital abnormality or birth defect

b. Reporting Requirements

All observed or volunteered adverse events occurring from the time of randomization to 30-days post randomization will be recorded in the subjects' case histories, regardless of the study group or suspected causal relationship. For all adverse events, sufficient information will be obtained in order to permit: 1) adequate determination of the seriousness, and 2) causal relationship of the adverse event. Adverse events or serious adverse events found to be a result of the treatment regimen will be followed until resolution of the adverse event.

Reportable adverse events include:

- Excessive Bleeding
- Hematoma
- Ischemia
- Infection
- Rash at access site

All adverse events and serious adverse events are to be reported to the Aurora Health Care Internal Review Board as outlined in the applicable policies.

c. Assessment of Relationship

The Principal Investigator is responsible for assessing the relationship of the adverse event or serious adverse event to the treatment.

IX. Data Analysis and Review

Continuous variables will be presented as means and standard deviation or median and interquartile ranges if normality is not assumed. Baseline demographic and medical data will be summarized and compared by standard descriptive statistical methods (ANOVA for continuous variables and Chi squared test for categorical variables or their non parametric equivalents). Comparisons will be made among groups based upon clinical factors using univariate regression to select potential independent predictors of outcomes (as defined in section III of the current document). Relevant potential independent predictors as determined by univariate analyses and expert clinical knowledge will then be included in multivariate regression models. Assumptions and goodness of fit will be assessed for each model. Statistical significance will be defined as a two tailed p value < 0.048 at final analysis. Further data analysis will be performed by clinical statistician (TBD).

A stratified analysis by French size or procedure type will be considered if there is evidence to suggest one is needed.

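### Randomised patients can be withdrawn as screen failures; if the procedure includes closure, the rule removes figure-8 complications but not comparable ProGlide ones, and no analysis set restores them

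*Combined protocol and SAP*

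**What the plan says.** Section III (Randomization) has the investigator draw the envelope "only after sheath access has been achieved with no complications". The envelope decides between ProGlide and figure-8 suture, so it must be opened before closure.

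Three rules can then remove a patient:

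- **Complication rule.** Section III: "if a complication not related to the Perclose ProGlide SMC closure device happens during the procedure the subject will be withdrawn from the study", and the patient is counted as a screen failure. Section IV repeats it as an exclusion criterion: "Patients who have complications during the procedure not related to the Perclose ProGlide SMC closure device".
- **Method-switch rule.** Section III: if at any time "the physician decides to use an alternate standard of care method as the primary method to achieve hemostasis" in place of the assigned one, the patient is a screen failure. Section IV repeats this too.
- **Access-site bleeding rule.** Section IV excludes "Patients with intra-procedural bleeding around access site".

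Only the complication rule exempts one arm's device. The other two are worded the same for both arms.

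Section VIII.b states that "adverse events occurring from the time of randomization to 30-days post randomization will be recorded", whatever the group. Section XIII(f) asks for the reason for each withdrawal to be documented. Sections IX and X name no intention-to-treat, per-protocol or safety set and do not say how randomised screen failures are analysed.

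**The concern.** A screen failure is normally a patient who never reaches randomisation. Here the label is applied to patients already allocated, for reasons tied to how the procedure or the closure went. Dropping them can break the comparability that randomisation provides.

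The complication rule adds a possible arm imbalance. Section VII lists hematoma, bleeding and vessel rupture among the risks of figure-8 suture. In a figure-8 patient such an event cannot be related to ProGlide, so it would meet the withdrawal condition if closure counts as part of the procedure. The same event caused by ProGlide in the other arm would not.

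Comparing safety is part of the primary objective, and section XI lists bleeding, hematoma and vascular injury among the secondary outcomes. No passage says who decides relatedness for withdrawal. For adverse events, section VIII.c says "The Principal Investigator is responsible for assessing the relationship of the adverse event or serious adverse event to the treatment"; no blinding is described.

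**Working it through.** **1. When the rules bite.** Sheath access, then envelope, then closure. Any complication or switch after the envelope is post-randomisation. This needs no assumption.

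**2. Two readings of the complication rule.** *During the procedure* is not defined.

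- *Reading A: closure is included.* The documents use ProGlide only for closure, so its exemption has a clear purpose only on this reading. Figure-8 closure complications are withdrawn; comparable ProGlide ones are not withdrawn under this rule.
- *Reading B: the procedure ends before closure.* Section VII separates the two: "these complications may occur and/or be related to the procedure or the vascular closure". Closure complications then stay in both arms, but complications between envelope and closure still remove randomised patients.

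**3. Interaction with the other rules.** Under A, the bleeding exclusion would also cover bleeding at closure, in either arm, and the method-switch rule can remove either arm's closure difficulties. Both overlap with the ProGlide exemption: a ProGlide-related bleed is spared by one rule and removed by another. The passages must be reconciled.

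**4. The plan's own figures.** Section X takes 101 subjects plus about 10% to 110. 101 × 1.10 = 111.1 and 101 / 0.90 = 112.2, both close to 110. That allowance replaces numbers; it does not correct for which patients are lost. The documents give no complication rate, so the rest is an illustration.

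**5. Reported rates.** Let p be the true closure-complication risk, equal in both arms, and s the share of those patients withdrawn. The reported rate is p(1 − s) / (1 − ps). At p = 10%:

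- s = 0: 10.0%
- s = 0.25: 0.075 / 0.975 = 7.7%
- s = 0.5: 0.05 / 0.95 = 5.3%

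Removing half of the figure-8 events takes out 55 × 0.10 × 0.5 = 2.75 patients on average.

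**6. Chance of a false finding that ProGlide is worse.** Inputs: 55 per arm (section X), two-sided p < 0.048 (section IX). Assumed: Fisher's exact test on the patients kept, and equal true risk. All outcomes were enumerated exactly. The one-sided nominal level for comparison is 0.048 / 2 = 2.4%.

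| Share of events removed (ProGlide / figure-8) | p = 2% | 5% | 10% | 15% |
|---|---|---|---|---|
| 0 / 0 | 0.03% | 0.4% | 1.0% | 1.3% |
| 50% / 50% | 0.00% | 0.15% | 0.75% | 1.2% |
| 25% / 50% | 0.02% | 0.6% | 2.9% | 5.0% |
| 0 / 50% | 0.05% | 1.6% | 7.5% | 14.1% |
| 0 / 100% (extreme) | 0.08% | 5.6% | 47.6% | 85.2% |

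With a further 5% risk of later events, kept in both arms:

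| Share removed (ProGlide / figure-8) | p = 2% | 5% | 10% | 15% |
|---|---|---|---|---|
| 0 / 0 | 0.7% | 1.0% | 1.2% | 1.3% |
| 50% / 50% | 0.8% | 1.1% | 1.3% | 1.5% |
| 0 / 50% | 1.2% | 2.8% | 6.8% | 11.4% |

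Equal removal stays below 2.4% throughout. The error comes from imbalance between arms.

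**The case against.** The strongest reply is that reading B has more text behind it. The title, the objective and the hypothesis all place closure after the venous access procedure, the background treats access-site bleeding and hematoma as post-procedure complications, and section XI words major bleeding as a post-procedure event. Support for reading A is an inference from the purpose of the exemption. Further, if A is applied consistently, the arm-neutral bleeding exclusion removes ProGlide bleeds as well, so the fully one-sided scenario fits the protocol's own rules poorly.

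Other fair points:

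- The outcomes most exposed are secondary.
- Taken alone, the rule works against the device, so it does not manufacture the hypothesised benefit.
- Background section I describes a low incidence of vascular complications with ProGlide, and at 2% risk the illustrated effect is negligible.
- Adverse-event recording from randomisation and documented withdrawal reasons should leave much of the safety information available.

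Most of this stands as a limit on size. It does not remove the defect. Under reading B, and under the method-switch rule on any reading, randomised patients still leave the study for reasons that may be linked to outcome. The recording rules say what is written down, not who is analysed.

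**Conclusion.** The concern holds and should be fixed before analysis. On either reading, the plan lets randomised patients be withdrawn as screen failures after allocation, and no stated analysis set restores them. The imbalance against ProGlide is conditional on reading A.

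Its size cannot be derived from the documents. Under the assumptions in the working, it is negligible at 2% risk and large only from about 10% risk with clearly one-sided removal. The bleeding and method-switch rules may shrink it, so the net direction of all three rules together is unknown. Equal removal gives no false difference but understates the complication rate in both arms.

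The complication rule does not reach events after the procedure. Any effect on time to hemostasis or time to ambulation is of unknown size; slow closure alone does not trigger withdrawal, because supplemental compression is allowed in both arms. Confidence is medium because the key term is undefined.

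**What to change.** - Limit withdrawal and screen failure to events before the envelope is opened.
- State that the complication, access-site bleeding and method-switch criteria do not remove a randomised patient from the analysis. The physician's freedom to switch method is unaffected.
- Continue outcome collection to day 30 for every randomised patient, and analyse time to hemostasis, time to ambulation, bleeding, hematoma, vascular outcomes and adverse events by assigned arm.
- Define *during the procedure*, say who judges relatedness, and word relatedness to the assigned closure method identically for both arms.
- Report the number removed or switched, with reason, by arm.

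The cost is wording in sections III, IV and IX. Section VIII.b already requires adverse-event recording from randomisation to 30 days; add that this and outcome collection continue for randomised patients now called screen failures. The downside is some added noise in both arms from unrelated procedural complications and method switches.

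### Randomized patients whose primary closure method is switched are classed as screen failures, and no analysis set keeps them in the comparison

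*Combined protocol and SAP*

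**What the plan says.** Section III (Randomization) has the investigator draw the envelope "only after sheath access has been achieved with no complications", that is, before closure. At any time afterwards the physician may turn to a different standard-of-care method as the primary means of hemostasis, "other than that which the patient was randomized to, they may do so, and the patient will be considered a screen failure". Section IV lists among the exclusions that the physician must "use an alternate method as the primary venous closure method other than that which the patient was randomized to". The two thresholds differ slightly (a decision in Section III, a necessity in Section IV), but both presuppose an assignment already made.

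The rule has a limit. In both arms "supplemental manual compression may be used following device/suture placement if needed", so a closure helped by compression is not a switch.

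Three other provisions touch these patients:

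- Section VIII.b: "All observed or volunteered adverse events occurring from the time of randomization to 30-days post randomization will be recorded", whatever the group. This governs recording, not who is analysed.
- Section XIII, item f: reasons for withdrawal are to be documented. Reporting by arm is not mentioned.
- Sections IX and X: tests, regression models, significance level and sample size are given, but no intention-to-treat, per-protocol or as-treated set.

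Two further rules are unclear as to timing. Section III says that "if a complication not related to the Perclose ProGlide SMC closure device happens during the procedure the subject will be withdrawn from the study", with screen-failure status. Section IV excludes "Patients with intra-procedural bleeding around access site" and patients given low-molecular-weight heparin (LMWH) within a window that extends past the procedure. Neither section says whether these rules act once the envelope has been opened.

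**The concern.** A screen failure is ordinarily someone who never reached randomization. Here the label covers people who were randomized and then departed from their assignment, through a decision made by someone who knows the arm. One reason to abandon a closure method is that it is not achieving hemostasis, and such cases bear directly on TTH, TTA and bleeding. A comparison of closure strategies could therefore leave out patients in whom a strategy failed.

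Two conditions are needed for bias in the mean difference: switching must differ between the arms, and it must be related to outcome. The plan offers no assurance on either. It does not commit to reporting switches by arm, so the published comparison need not show whether the conditions were met.

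**Working it through.** **What the plan's figures allow.** The rule has no figure of its own. The required 101 patients cannot be rebuilt, because Section X names no effect size, SD or powered outcome. Section X then says "A 10% +/- should be added, to bring the total enrollment to 110 subjects". The addition is 110 − 101 = 9 patients; its purpose is not stated. Nine removals serve below only as a scale, not as an estimate of switching.

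**Inputs from the plan.** 1:1 allocation with 110 envelopes (Section III), hence 55 per arm; two-sided 0.048 at the final analysis (Section IX).

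**Assumptions.** No true difference; outcome y distributed N(0,1) in both arms; longer times more likely to be removed. Each patient has a score s = ρy + √(1−ρ²)·e, with e an independent N(0,1). The k patients with the highest s in an arm are removed, and a t-test at 0.048 is run on the rest (40,000 runs per cell). The correlation ρ is 0 if switching is unrelated to outcome and 1 in the worst case.

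**Type I error (nominal 0.048)**

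| Removed (arm A–arm B) | ρ=0 | ρ=0.5 | ρ=0.8 | ρ=1 |
|---|---|---|---|---|
| 3–3 | 0.047 | 0.051 | 0.058 | 0.068 |
| 3–0 | 0.047 | 0.059 | 0.079 | 0.101 |
| 6–0 | 0.049 | 0.081 | 0.140 | 0.207 |
| 5–4 | 0.050 | 0.054 | 0.068 | 0.079 |
| 6–3 | 0.048 | 0.061 | 0.085 | 0.106 |
| 7–2 | 0.050 | 0.073 | 0.113 | 0.164 |
| 9–0 (extreme) | 0.047 | 0.112 | 0.231 | 0.349 |

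The simulation standard error near 0.048 is √(0.048 × 0.952 / 40,000) ≈ 0.001.

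**Check on the mean shift.** For a removed fraction q = k/55, the mean of those kept falls by about ρ·φ(c)/(1−q), where c is the (1−q) normal quantile. For 6 removed this is 0.210ρ and for 3 it is 0.117ρ. The 6–3 shift at ρ=1 is therefore about −(0.210 − 0.117) = −0.093 SD; the simulation gave −0.092. With 3–3 the two shifts cancel. With ρ=0 there is no shift at any split.

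**Milder cases.** At ρ=0.3: 1–0 gives 0.048, 2–0 gives 0.049, 2–1 gives 0.048 and 3–0 gives 0.051. At ρ=0.5: 1–0 gives 0.049 and 2–1 gives 0.053.

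**Sensitivity to the test.** For the 6–3 split over the same four correlations, a rank-sum test gives 0.048 / 0.059 / 0.080 / 0.097. A t-test on lognormal times (SD of log = 1) gives 0.041 / 0.054 / 0.099 / 0.194.

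**The case against.** The best reply is that no harm is shown in this trial. Removal from the analysis is inferred rather than stated; switch rate, direction and link to outcome are all unknown; and the milder cases above show almost no inflation. The rule is also narrower than it looks: supplemental compression keeps slow closures in, and a switch made before any closure attempt need not relate to outcome. Adverse events are still recorded from randomization, withdrawal reasons are documented, and the variable list is in an attached file not available here, so switches may already be captured.

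Most of this stands as a limit on size. The table shows a mechanism and forecasts nothing, and its largest cells are the least supported. It does not remove the point. Recording an event or a reason does not place a patient in the TTH and TTA comparison, and capturing a switch is not a commitment to report it by arm. If the sponsor means to analyse everyone randomized, the plan needs to say so.

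It may also be said that barring every removal after the envelope is opened is too broad, since it retains patients later found ineligible. That is ordinary intention-to-treat practice, and a per-protocol analysis remains available for the narrower question.

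**Conclusion.** The concern holds and should be resolved before the final analysis. Followed as written, the plan labels randomized patients screen failures because of an arm-aware decision made after allocation, and nothing returns them to the comparison of either primary outcome. The weight of the point rests on the loss of the randomized comparison, not on an assumed switch rate. Depending on the number removed, the imbalance and the correlation with outcome, type I error in the illustration runs from no inflation to 0.349 in the extreme cell. No direction is claimed, and no size is given for the safety outcomes.

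The two timing ambiguities are not needed for this conclusion but should be reconciled. If the complication rule acts after the envelope is opened and closure counts as part of the procedure, it would remove suture-related complications while keeping Perclose-related ones. The access-site bleeding and LMWH exclusions likewise need a stated time of application.

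**What to change.** 1. In Sections III and IV, limit screen failure to patients whose envelope was not opened, and state that no exclusion removes a patient from analysis after that point. This also settles the timing ambiguities for the analysis.
2. In Section IX, define the primary analysis set as all randomized patients, analysed in the assigned arm for TTH, TTA, time to discharge and safety to 30 days.
3. Leave the physician's freedom to switch as it is. Record each switch, and report switches and withdrawals by arm and reason.
4. For switched patients, state the time zero for TTH and TTA. The TTA definition in Section XI starts the treatment-arm clock at removal of the final Perclose device, which gives no start when that device was assigned but not used. Leave the definitions otherwise unchanged.
5. Keep the present set as a per-protocol sensitivity analysis.

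**Cost.** Wording changes, plus data retrieval. Section X refers to a completed interim analysis, so the trial was under way; data on patients already withdrawn would have to come from the medical record where consent permits, which cannot be judged here.

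The statistical price is dilution. With 55 per arm and two-sided 0.048, a t-test has 80% power at d = 0.542 SD. If k patients in one arm switch and take the other arm's mean, the difference becomes d(1 − k/55):

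| k | Diluted difference (SD) | Power |
|---|---|---|
| 3 | 0.51 | 75% |
| 6 | 0.48 | 70% |
| 9 | 0.45 | 65% |

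These counts are assumptions. If they are thought realistic, the sample size should be reconsidered.
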